**Randomization to Stage 2 Treatments for LDX and CBT+LDX (Stage 1) “Responders”.**

“Responders” to Stage 1 LDX (i.e., LDX and CBT+LDX) treatments will be defined as 65% or greater reduction in binge-eating. This cut-point is based on reliable findings regarding prognostic significance of such reductions ([name] et al., 2006; 2012) and supported by recent report on “time course of the effects of LDX” (McElroy et al., 2017). “Responders” will be randomized in equal proportions (using stratified blocked randomization with Stage 1 treatment as a stratifying variable) to LDX or placebo (double-blind) for 12 weeks.

**CBT Treatment Protocol.** CBT will be delivered by trained and monitored research clinicians following manualized protocols we have used successfully in previous RCTs (e.g., [name] et al., 2005, [name] et al., 2011). CBT will be delivered in individual sessions weekly for 12 weeks following CBT manuals based on Fairburn et al (1993) used in our RCTs ([name] et al., 2005, 2011) which are similar to those used in major RCTs testing CBT delivered via 12-24 weeks (Wilfley et al., 2002; Wilson et al., 2010). The CBT manuals provide detailing session-by-session procedures for clinicians and parallel guides are provided to the patients to facilitate homework and mastery of the material. CBT, a specialist focal treatment, consists of

three overlapping phases. Phase one involves establishing a collaborative therapeutic relationship while focusing on educating the patient about the nature of binge-eating and factors thought to maintain the problem. Specific behavioral strategies (e.g., self-monitoring) are used to help patients identify problematic eating patterns while establishing a normal structured eating pattern. Phase two integrates cognitive restructuring procedures, where patients learn to identify and challenge maladaptive cognitions regarding eating and weight/shape and thoughts that trigger binge-eating. Phase three focuses on maintenance of change and relapse prevention.

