#### **Assessment of Treatment Outcome and Time Course.**

Primary Measures: (1) Binge-eating frequency (EDE); (2) weight (measured weight and height and BMI); for Stage 2 LDX vs Placebo test: "Relapse" to DSM-5 threshold of once-weekly binge eating on EDE

Secondary Measures: (1) "remission" (zero binges past 28 days on EDE; eating disorder pathology (EDE global), depression (BDI-II); for exploration of mediators: (2) eating behaviors (EDE, TFEQ, FCI-II), executive control and impulsivity (BIS-11, DDT, Trails) and selected metabolic measures (lipid profiles, HbA1c, blood pressure, HR) to characterize metabolic outcomes and allow comparison with RCTs for LDX and NB.

**Figure 2.** Grid depicting when each measurement is obtained

Assessment Points	BASELINE (2 MTG)	DURING RX STAGE 1 1-MONTH	DURING RX STAGE 1 2-MONTH	POST RX STAGE 1 3-MONTH	DURING RX STAGE 2 4-MONTH	DURING RX STAGE 2 5-MONTH	POST RX STAGE 2 6-MONTH	6 AND 12- MO FOLLOW- UP (18 MONTH TOTAL)
MINI Psychiatric Interview, Height, Credibility,	•							
EDE Interview, SF-12, GPAQ, Lipid Profile, HbA1C, Glucose	•			•			•	•
EDE-Q-I, BDI-II, GLTEQ, Weight, BP, HR	•	•	•	•	•	•	•	•
TFEQ-Restraint	•	•		•			•	•
DDT	•	•		•			•	
FCI-II, PFS	•	•		•	•		•	
BIS-11	•	•		•	•		•	•
ELOCS	•	•		•				
Trails, YFAS, BRS, Amphetamine Testing	•			•			•	
Placebo Ratings					•		•	
Start of New Treatments				•			•	•
Medical History Creatinine w/ EGFR PSQI	•			•				
Adverse Events		•	•	•	•	•	•	
Insulin	•			•				

Liver Function	•			•	• (Non- responde rs only)			
Pregnancy Test	•			•				

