### DATA ANALYSIS

Baseline demographic and clinical characteristics for randomized groups will be compared using chi-square tests for categorical variables, and ANOVA or Kruskal-Wallis tests for continuous variables. Continuous variables will be examined for adherence to normal distribution using normal probability plots and Kolmogorov-Smirnov tests. If normality not satisfied and transformations do not help with achieving normality, alternative analytic strategies will be considered such as generalized estimating equations or nonparametric methods. Dropouts and completers will be compared. Analyses will be intent-to-treat; patients will be followed regardless of treatment completion to minimize missing data. Primary outcomes will be tested at two-sided 0.05 significance level. Secondary analyses will be adjusted for multiple tests using Bonferroni correction.

Overall Data Analysis Strategy will involve MIXED EFFECTS MODELS (Diggle et al, 2002, Gueorguieva & Krystal, 2004) to compare treatments. These models allow for different numbers of observations per subject, use all available data on each subject, and are unaffected by randomly missing data. Further advantage is capacity to test and account for individual-difference contributions to treatment outcomes (Cudeck, 1996; Cudeck & Klebe, 2002; Hedeker et al., 1996; Hedeker & Gibbons, 1996; Singer, 1998). They provide flexibility in modeling the correlation structure of data. In models for each outcome, we will include fixed effects of time, treatment, and interaction between time and treatment, and random subject-level effects. Because we cannot a priori predict the shape of responses over time in each arm of the trial we will first treat time as a categorical predictor and will then test for polynomial trends over time. We will consider different error structures (e.g., AR1, independence) and select the best fitting one based on information criteria. We will

compare dropout patterns between groups and if there are concerns of informative dropout or informative intermittent missing data, we will use pattern mixture models (Hedeker & Gibbons, 1997) to perform sensitivity analyses.

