Finally, we expect that “rapid response” will have differential prognostic significance for CBT and LDX. Based on our prior methods ([name] et al., 2006; [name], White, et al., 2012; Masheb & [name], 2007), we hypothesize that overall rapid response will predict superior outcomes in both treatments (i.e., greater weight losses in LDX and greater reductions in binge-eating in both CBT and LDX) and that non-rapid-response will predict no further improvement in LDX but not for CBT (where gradual improvement is expected). In terms of mediators, per Kraemer et al (2002) models, we will explore whether differential symptom changes during treatment are associated with subsequent longer-term primary outcomes (binge-eating and weight loss). Repeated (and early) assessments of eating behaviors and cognitions (EDE-Q-I, TFEQ) constructs relevant to CBT, food-reward constructs (FCI-II, PFS) and executive control (Trails, BIS, DDT) constructs relevant to LDX, food-reward (FCI-II, PFS) constructs relevant to NB, and more general conceptually supported constructs (depression (BDI-II)), will yield relevant change variables for analyses of mediation (i.e., testing subsequent changes in binge-eating and weight). These analyses are exploratory and hence may be underpowered. However, they will provide valuable information in the form of variability estimates and effect size estimates for future more definitive studies.

(3) **STAGE 2 – Primary Aim 1:** Among Responders to Stage 1 treatments with LDX (i.e., LDX and CBT+LDX), compare LDX to placebo as a treatment maintenance strategy. The primary outcome will be “relapse” to DSM-5 level of once-weekly binge-eating and secondary outcomes will be binge-eating frequency, weight loss, eating-disorder pathology, and depression. For the primary outcome (predicting relapse), we will follow

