analytic strategy of studies testing medication for maintenance (i.e., fluoxetine) for bulimia nervosa (Romano et al (2002) and for anorexia nervosa (Walsh et al (2006) which was recently used in the Shire maintenance study of LDX for BED (Hudson et al., 2015). Stage 2 LDX and placebo will be compared on the proportion of Stage 1 responders who “relapse” using chi-squared tests and Cox Proportion Hazards Tests; we will explore further using survival analyses to estimate whether time to relapse differs between LDX and placebo. For the secondary outcomes, we will use mixed effects models to assess whether there is significant change in binge eating or weight loss between the group who continue LDX treatment and the group who receive placebo. We anticipate that subjects randomized to LDX maintenance will maintain better outcomes than patients randomized to placebo. We will also perform parallel analyses on all three groups (CBT, LDX, CBT+LDX) to compare outcomes at the 6-month time point (i.e., comparing 3-month CBT and 6-month two-stage treatments).

(4a) **STAGE 2 – Secondary Aim 1:** Explore LDX and CBT effects, alone and in combination, for longer-term BED outcomes. Our two-stage design will also allow us to also compare CBT (i.e., Stage 1 CBT-only short-term) versus the Stage 2 LDX/placebo maintenance treatment (i.e., Stage 2 LDX/placebo following Stage 1 LDX or Stage 1 CBT+LDX) for longer-term outcomes through 18 months. This will inform clinical questions regarding whether LDX maintenance treatment following either acute LDX treatment or acute combined CBT+LDX differ and whether it offers any additional benefits over acute CBT-only (4b).

**STAGE 2 – Secondary Aim 2:** Among Non-responders to Stage 1 treatments with LDX, Explore the effectiveness of switching to an alternative medication (NB versus placebo). Primary outcomes will be reducing binge-eating and reducing weight and secondary outcomes will be binge-eating remission, eating-disorder pathology, and depression. We will use similar analyses to Primary Aim 1: mixed models for the continuous outcome variables and logistic regression for categorical (remission) variable.

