**(5) Secondary Aim:** Generate estimates of cost-effectiveness. We will compute within-study costs for CBT, LDX, CBT+LDX and SMART Stage 2 interventions. Repeated assessments will track additional clinician visits and medication use in our RCT as well as outside treatment contacts through the 18-months. SF-12, administered pre- and post-treatments and at follow-ups, will be used to calculate quality-adjusted life years (QALY) following established methods (Revicki et al., 2005) also used in BED studies of cost-effectiveness specifically of LDX (Agh et al., 2016) and CBTgsh (Lynch et al., 2010; Dickerson et al., 2011), as well as for obesity (Tsai et al., 2005; Malone et al., 2005) including obesity medications (Ara et al., 2012), and for similar SMART designs (switching medication for initial non-responders) in depression (Singh et al 2017). We will calculate incremental cost-effectiveness ratios (ICERs) for the various arms; in these ICERs, the numerator will be the incremental medical cost and the denominator will be the incremental effectiveness of the specific treatment compared to CBT. Confidence intervals for the ICERs will be determined using non-parametric bootstrapping. These ICERs will be compared to the two previous BED (Agh et al., 2016; Lynch et al., 2010) analyses and inform subsequent more definitive larger-scale effectiveness studies.

**POWER ANALYSIS:** We calculated our sample size to have at least 80% power at 2-tailed alpha level 0.025 (adjust for 2 outcomes) to detect clinically meaningful effects in Stage 1 for co-primary outcomes (binge eating and weight loss) and Stage 2 for primary outcome (relapse by initial Responders) at 2-tailed level of 0.05 according based on documented effects of the two treatment components (LDX and CBT). In Stage 1, with 180 subjects total (60 per treatment group), accounting for up to 20% dropout, we can detect medium effect sizes ( $d=0.64$ ,  $f=0.32$ ) for the between group comparisons with more than 80% power at two-sided alpha level of 0.025. These effect sizes are smaller than the effect sizes calculated based on data (Telch et al., 1990; [name] et al., 2005; McElroy et al., 2015, McElroy 2016) which ranged  $d=0.69$  to  $d=0.78$  for the comparison of CBT to LDX on binge-eating and was  $d=1.53$  for LDX vs CBT on percent weight loss. Dropout

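### The single Stage 2 primary outcome (relapse) is given two tests with neither named as deciding, and neither accounts for the randomisation stratum

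*Combined protocol and SAP*

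**What the plan says.** - **Outcome.** Under Assessment of Treatment Outcome and Time Course, the Stage 2 primary measure is relapse "to DSM-5 threshold of once-weekly binge eating on EDE". Data Analysis item (3) repeats the once-weekly threshold without a time point.
- **Tests.** Item (3) compares the proportions who relapse "using chi-squared tests and Cox Proportion Hazards Tests". After a semicolon it adds: "we will explore further using survival analyses to estimate whether time to relapse differs between LDX and placebo". Only that last part is labelled exploratory.
- **Alpha.** The opening paragraph of Data Analysis states: "Primary outcomes will be tested at two-sided 0.05 significance level". The Power Analysis repeats this for "Stage 2 for primary outcome (relapse by initial Responders) at 2-tailed level of 0.05". The multiplicity rule covers other analyses only: "Secondary analyses will be adjusted for multiple tests using Bonferroni correction".
- **Randomisation.** Responders are allocated 1:1 to LDX or placebo "using stratified blocked randomization with Stage 1 treatment as a stratifying variable", so the strata are LDX and CBT+LDX. Item (3) mentions neither stratification nor adjustment. The general mixed-model strategy lists only time, treatment and their interaction as fixed effects.
- **Schedule.** Within Stage 2, Figure 2 places the EDE interview only at month 6. Months 4 and 5 have the self-report EDE-Q-I.

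**The concern.** Three things are left open for a primary comparison.

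1. Which test decides. With about 64 completers, chi-squared and Cox can fall on opposite sides of 0.05, and the plan does not say which result then stands.
2. What Cox would be run on. The outcome's instrument is used once in Stage 2, so event times either do not exist or come from something outside the stated definition.
3. Whether the analysis follows the randomisation. The stratum is used to allocate patients and then disappears from the test.

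At stake is a confirmatory claim about maintenance treatment whose test could be chosen after the data are seen. The size of the resulting error has to be checked, because the two tests share the same events.

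**Working it through.** **1. The plan's own figure.** Inputs from the Power Analysis: about 80 responders, 20% dropout, so 80 × 0.8 = 64, or 32 per arm; relapse 4% vs 32%; two-sided 0.05; stated power 89%.

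Arcsine formula: h = 2·asin(√0.32) − 2·asin(√0.04) = 1.2025 − 0.4027 = 0.7998. Power = Φ(h·√(32/2) − 1.960) = Φ(3.199 − 1.960) = Φ(1.239) = 89.2%. The exact binomial power of the uncorrected Pearson chi-squared is 89.3%. The 89% thus fits one unstratified two-proportion test at 0.05.

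**2. Either-test error, relapse read only at month 6.** All events fall at one time, and patients without a month-6 EDE drop out of both tests. The log-rank (Cox score) statistic is then the Pearson statistic times (N − 1)/N, here 63/64. It cannot reject when Pearson does not, so the either-test error equals that of chi-squared alone. Simulation agrees: 4.4-5.8% for both (40 per arm, equal relapse of 18, 32 or 45%, dropout 0 or 20%).

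**3. Either-test error, intermediate event dates.** The dates and null relapse rates here are assumptions.

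| Setting | Chi-squared alone | Either test |
|---|---|---|
| Both tests on the same patients and events; 32 or 40 per arm; relapse 18 or 32%; continuous or monthly dates; dropout 0 or 20% | 4.5-5.7% | 5.1-6.1% |
| Completer chi-squared, log-rank also using dropouts' partial follow-up; 40 per arm; relapse 18-45%; dates in about 10-day steps; 20% dropout | 4.4-5.6% (each test) | 6.4-6.9% |

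In the first setting the excess over chi-squared alone is 0.0-1.1 points, and the tests disagree in 0.4-2.0% of null trials. With a completer chi-squared and monthly dates they disagree in 2.6-3.1%.

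**4. Effect of omitting the stratum.** Take equal strata with relapse pA and pB, and treatment balanced within each. The true variance of the difference is proportional to the mean of p(1 − p) over strata, whereas the unstratified test uses p̄(1 − p̄), which is larger. With ratio r, the approximate size is 2·[1 − Φ(1.960/√r)].

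| pA / pB (assumed) | Mean p(1−p) | p̄(1−p̄) | r | Approximate size | Simulated size, unstratified | Simulated size, CMH |
|---|---|---|---|---|---|---|
| 10% / 30% | 0.15 | 0.16 | 0.938 | 4.3% | 4.5% | 4.9% |
| 10% / 50% | 0.17 | 0.21 | 0.810 | 2.9% | 3.2% | 5.2% |
| 20% / 60% | 0.20 | 0.24 | 0.833 | 3.2% | 3.7% | 5.4% |

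When the strata differ, the either-test error is also below 5% (3.5-4.8%).

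**5. Power after the change.** Simulated CMH power at 4% vs 32% with 32 per arm is 89.4-89.8%; its size with equal strata is 4.5-5.6%.

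**6. The alternative of splitting alpha.** Pooled formula: Φ{[0.28 − z·√(2·0.18·0.82/32)]/√[(0.04·0.96 + 0.32·0.68)/32]}, with denominator 0.0894. At z = 1.960 the numerator is 0.0918, giving Φ(1.026) = 84.8%. At z = 2.241 (0.025 each) the numerator is 0.0647, giving Φ(0.724) = 76.5%.

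**The case against.** The strongest reply is that this is a small ambiguity with an evident intended answer. The only powered Stage 2 comparison is a difference in proportions at the end of Stage 2, and the 89% reproduces as one such test. The 0.05 is assigned to the primary outcome, not to each test, and no sentence says that success on either test is enough. Much of the larger excess comes from pairing a completer chi-squared with a Cox test that also uses dropouts; the plan says intent-to-treat and does not specify a completer analysis.

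All of that stands as to size. It does not settle which test decides, because the text puts Cox beside chi-squared and labels only the further survival analyses as exploratory.

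Stronger readings that a reader might infer, and why they fail:

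- *Two tests at 0.05 give 1 − 0.95² = 9.75%.* That requires independent tests. These use the same events and rarely disagree.
- *Ignoring the strata raises false positives.* The direction is the reverse (working, step 4).
- *Stage 1 treatment is a strong known predictor of relapse.* The documents report no relapse rates by prior CBT, and secondary aim 4a treats the difference as an open question.
- *Cox might run to month 18.* With EDE visits at months 6, 12 and 18 and chi-squared at month 6, simulation gave 7.4-8.7%. The aim does mention longer-term outcomes, but the power statement refers to the end of Stage 2, so this is not the supported reading.

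**Conclusion.** The point holds as an unspecified primary test plus an analysis that does not follow the stratified randomisation. It does not hold as a serious inflation of error. If success on either test counted, the 5% error would rise by about 0 to 2 percentage points. The rise is zero on the plan's own EDE schedule. It reaches 6.4-6.9% in total only with assumed intermediate event dates, 20% dropout and a completer chi-squared. Omitting the stratum costs calibration in the conservative direction: a size of about 3-4.5% if relapse differs by Stage 1 treatment as assumed (10%/30% to 20%/60%, equal-sized strata), while the stratified test holds about 5%. The change is worth making because it settles the deciding result in advance and costs essentially no power.

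**What to change.** In Data Analysis item (3), name one deciding test at two-sided 0.05: the proportion relapsed at the end of Stage 2, on the month-6 EDE, by a Cochran-Mantel-Haenszel test stratified by Stage 1 treatment (LDX or CBT+LDX). Report a stratified risk difference with its 95% CI. State how randomised responders without a month-6 EDE are counted, since the gap between the two tests depends on it. Make Cox and time to relapse supportive, stratified in the same way, and say which instrument supplies the event dates.

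Fixing month 6 is itself a choice, because item (3) gives no time point. It matches the time point in the power statement and the only EDE visit within Stage 2; later EDE visits can be reported as longer-term outcomes.

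The cost is SAP wording only, with no extra data or patients. The stated 89% power is kept. Keeping both tests at 0.025 each would instead lower pooled-formula power from 84.8% to 76.5%.

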**STAGE 2 RCT – Secondary Aims:**

(4a) *Examine LDX and CBT effects, alone and in combination, for longer-term BED outcomes. Our two-stage design will allow comparison of CBT (i.e., Stage 1 CBT-only short-term) versus the Stage 2 LDX/placebo maintenance treatment (i.e., Stage 2 LDX/placebo following Stage 1 LDX or Stage 1 CBT+LDX) for longer-term outcomes through 18 months.* This will inform clinical questions regarding whether LDX maintenance treatment following either acute LDX treatment or acute combined CBT+LDX differ and whether it offers any additional benefits over acute CBT-only.

(4b) Among *Non-responders* to Stage 1 acute treatments with LDX (i.e., LDX and CBT+LDX), *explore the effectiveness of switching to an alternative medication NB vs placebo* for primary outcomes (reducing binge-eating and reducing weight) and secondary outcomes (binge remission, ED pathology, depression).

(5) Secondary Aims: Generate *cost-effectiveness* estimates of treatments. Incremental cost effectiveness ratios (ICERs) will be computed for LDX vs CBT and LDX+CBT vs CBT (using quality-adjusted life years).

2. **Probable Duration of Project:** State the expected duration of the project, including all follow-up and data analysis activities.

September 1, 2018- August 31, 2025

3. **Background:** Describe the background information that led to the plan for this project. Provide references to support the expectation of obtaining useful scientific data.

**SIGNIFICANCE:** Obesity (OB) is an increasingly prevalent, refractory, and serious public health problem, with estimates that 34% of U.S. adults are obese (Flegal, Carroll et al. 2010). Obesity is considered one of the most serious public health problems of the 21st century. Economic consequences of OB are staggering; associated annual medical costs were estimated at \$147 billion (roughly 10% of all medical spending) (Finkelstein et al. 2009), which reflects continued escalation since estimates of \$75 billion five years earlier (Finkelstein et al.

2004). This study focuses on testing treatments for a high-risk subgroup with binge-eating disorder (BED) (Hudson, Hiripi et al. 2007; Kessler et al., 2013).

Binge Eating Disorder (BED) – An Important Clinical Subgroup of Persons with Obesity

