**Pre-Screening:** Participants responding to recruitment efforts (see pages 35-36) will be screened by telephone. If participants prefer to answer some of the screening questions through the Yale Qualtrics system, participants will indicate their consent to the recruitment/screening process in the online system. Potentially eligible participants will be consented and evaluated in-person by trained supervised research clinicians (doctoral level and/or advanced trainees). Participants will complete survey measures of eating behaviors and psychopathology and psychosocial functioning around the time of the in-person appointment.

[figure not shown]
Participants who provide informed consent and are determined to be eligible (see page 15-16) will then participate in the study as depicted and described in the following paragraphs. See also Figure 1 (page 8).

**Stage 1**, N=180 patients with BED and obesity will be randomized to one of three 12-week treatments: CBT, LDX, or CBT+LDX.

**In Stage 2**, patients who received pharmacotherapy (Stage1 LDX or CBT+LDX) and were “Responders” (defined as 65% or more decrease in binge eating) will be randomly assigned in equal proportions (blocked randomization stratified by first treatment) to LDX or placebo (double blind) for 12 weeks.

“Non-responders” to Stage 1 pharmacotherapy (LDX or CBT+LDX) will be randomized to a second medication (NB or placebo) in double-blind fashion for 12 weeks. Stage 1 CBT patients will be followed without further treatment; this will allow controlled comparison of Stage 1 RCT and context for Stage 2 RCTs.

Independent assessments will determine outcomes after discontinuation of treatments through 18 months. Secondary aims are to produce important new data regarding predictors of outcomes and moderators of treatment effects to inform prescription (i.e., for whom LDX vs. CBT work best), and exploration of potential mediators through which the distinct treatments achieve outcomes, and cost-effectiveness estimates.

**Figure 1.** Study design

Potential participants will be screened by telephone and potentially eligible patients will be consented and evaluated in-person by trained supervised research clinicians (doctoral level and/or advanced trainees). (see page 36).

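### The month-6 comparison by Stage 1 arm averages the LDX arms over the Stage 2 re-randomisation, so it does not estimate any particular two-stage treatment

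*Combined protocol and SAP*

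**What the plan says.** The Stage 2 design is in Section I, item 4 (Research Plan). Responders in the two LDX arms "will be randomly assigned in equal proportions (blocked randomization stratified by first treatment) to LDX or placebo (double blind) for 12 weeks". Non-responders in those arms "will be randomized to a second medication (NB or placebo) in double-blind fashion for 12 weeks"; no ratio is given for them. For the third arm, "Stage 1 CBT patients will be followed without further treatment".

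The month-6 comparison is in item 13, Data Analysis (3), at the end of the paragraph on the Stage 2 primary aim. After the LDX-versus-placebo relapse analysis, the plan adds parallel analyses of all three Stage 1 groups at month 6, glossed as "comparing 3-month CBT and 6-month two-stage treatments". The overall strategy in Data Analysis gives the model terms: time, treatment, their interaction and random subject effects. It does not say how Stage 2 assignment enters.

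For cost-effectiveness, the Stage 2 secondary aims say that ratios "will be computed for LDX vs CBT and LDX+CBT vs CBT". Data Analysis (5) adds that "the denominator will be the incremental effectiveness of the specific treatment compared to CBT". It also lists the Stage 2 interventions, which it calls SMART, as items to be costed, and follows costs to 18 months.

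**The concern.** By month 6 each LDX arm contains up to four re-randomised groups: responders on LDX, responders on placebo, non-responders on NB and non-responders on placebo. Some non-responders are barred from the NB stage by exclusion criteria 20-22 (item 8) and form a further group. Comparing the whole arm with CBT averages over all of these.

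Aim 4a asks whether LDX maintenance after acute LDX or CBT+LDX adds anything over acute CBT. The plan also expects LDX maintenance to do better than placebo. If so, the pooled arm must look worse than continued LDX and better than LDX followed by placebo. A result labelled as six-month two-stage treatment could then be read as the result of six months of active treatment, which it is not.

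**Working it through.** **Inputs.** From Power Analysis: 60 per arm, so 120 in the two LDX arms; 65-70% responders; about 80 responders re-randomised, 64 analysed after 20% dropout (32 per group); relapse 4% on LDX and 32% on placebo; stated power 89% at two-sided 0.05. From Research Plan: 1:1 allocation of responders.

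**The plan's own figure.** It states no figure for the month-6 by-arm comparison. The nearest on the same inputs is the 89% power for relapse. For 4% vs 32% with 32 per group, exact enumeration of the uncorrected chi-squared test gives 89.3%, the arcsine approximation 89.2% and the unpooled normal approximation 87.9%. The figure is reproduced.

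**Who is on what in Stage 2.**
- Responders: 0.65 × 120 = 78 to 0.70 × 120 = 84.
- Assigned placebo at 1:1: 39 to 42, with the same number assigned LDX. So only 32.5-35% of an LDX arm is assigned LDX in Stage 2.
- Non-responders: 36 to 42. If NB:placebo were also 1:1 (an assumption) and all were re-randomised, 18 to 21 more would be on placebo, 60 of 120 in total.

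**Responder relapse, pooled.** 0.5 × 4% + 0.5 × 32% = 18%, against 4% if all continued LDX and 32% if all switched to placebo.

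**Response kept to month 6 over the whole arm** (responder share × (1 − relapse)):

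| Responders | Continued LDX | Pooled | LDX then placebo |
|---|---|---|---|
| 65% | 0.65 × 0.96 = 62.4% | 0.65 × 0.82 = 53.3% | 0.65 × 0.68 = 44.2% |
| 70% | 0.70 × 0.96 = 67.2% | 0.70 × 0.82 = 57.4% | 0.70 × 0.68 = 47.6% |

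The gap is 9.1 to 9.8 points in each direction. The CBT value cancels: (pooled − CBT) − (continued − CBT) = pooled − continued. So the contrast with CBT shifts by that amount whatever CBT achieves on this measure.

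**Other rate pairs in Power Analysis**, taking the lower rate as LDX; gap = responder share × half the difference:
- 10% vs 39%: 9.4 to 10.2 points
- 15% vs 46%: 10.1 to 10.9 points
- 25% vs 58%: 10.7 to 11.6 points

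**Cost-effectiveness ratios.** Let c1, e1 be the Stage 1 increments over CBT and c2, e2 those added by full active Stage 2 treatment. Pooling at one half gives (c1 + 0.5c2)/(e1 + 0.5e2), against (c1 + c2)/(e1 + e2). In invented units, (c1, e1, c2, e2) = (1, 1, 1, 2) gives 1.5/2 = 0.75 against 2/3 = 0.67. With (1, 1, 1, 0.5) it gives 1.5/1.25 = 1.20 against 2/1.5 = 1.33. The direction is not determined.

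**The case against.** The strongest reply is that comparing randomised Stage 1 groups is a sound intention-to-treat contrast, and that which estimand to report is a design choice. That stands. A reader might infer that the analysis is biased against LDX. The documents do not support this: the pooled figure understates continued LDX but overstates LDX then placebo by the same amount. What is missing is a statement of which quantity is meant.

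The month-6 comparison is also supplementary. The Stage 2 primary analysis compares LDX with placebo directly in responders, and the NB-versus-placebo analysis does the same in non-responders. This limits the harm, but neither gives a comparison of a full two-stage strategy with CBT. Aim 4a does not say whether its LDX/placebo maintenance group is pooled or split. Setting responders on one Stage 2 drug against all CBT patients would add responder selection.

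A reader might also infer that the cost-effectiveness ratios certainly pool the Stage 2 branches and thereby disfavour LDX. Neither part is established. Data Analysis (5) costs Stage 2 interventions as separate items and may intend separate ratios; if it does pool, cost and effect are both diluted.

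Nor does understatement against CBT follow for the mediator and rapid-response analyses. They are exploratory, they relate change or early response to outcome, and the rapid-response hypothesis is tied to no time point after month 3.

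Finally, the arm-level measure is constructed here, since the plan defines relapse for responders only. It counts every non-responder as a failure and ignores dropout and any NB effect. That is fair, and the size is illustrative.

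**Conclusion.** The point holds for month 6. As written, the by-arm comparison estimates the policy of starting LDX and then being re-randomised, not a two-stage treatment, and it cannot answer the plan's question about LDX maintenance against acute CBT. On the plan's main rates the difference is about 9-10 percentage points of kept response in either direction, and up to 11.6 with its other rate pairs. This rests on 65-70% responders, 1:1 allocation of responders, the plan's assumed relapse rates, non-responders counted as failures and no dropout.

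Allocation of half to placebo is documented for responders only; for non-responders it is an assumption. For cost-effectiveness the finding is that the handling of Stage 2 branches is unspecified, with no direction of bias claimed. The primary tests in both stages are unaffected.

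**What to change.** Keep the by-arm month-6 result and label it as an average over Stage 2 assignment. Add month-6 estimates of the strategies embedded in the design, each compared with the whole CBT arm:

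- LDX (or CBT+LDX), then assigned active Stage 2 drug if re-randomised;
- LDX (or CBT+LDX), then assigned placebo if re-randomised.

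Weight each re-randomised participant whose assignment fits the strategy by the inverse of the actual allocation probability: 2 for responders and, for non-responders, whatever follows from the NB:placebo ratio used, which the plan should state. Give weight 1 to CBT participants and to LDX-arm participants who were not re-randomised, including those barred under exclusion criteria 20-22. Use robust standard errors. The weighting restores responders and non-responders to their shares of the full arm and so avoids responder selection.

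Apply the same approach to any cost-effectiveness ratio that runs beyond month 3, or state that Stage 2 branches are separated. In mediator or rapid-response models, at most include Stage 2 assignment as a covariate when the outcome falls after month 3.

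This needs SAP wording and a weighted analysis of data already collected; randomisation and visits do not change. The price is precision. Each strategy rests on about half of the re-randomised participants: about 0.5 × 60 = 30 per LDX arm if everyone is re-randomised 1:1, before dropout. Intervals will be wider than for the by-arm result.
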